1.4 Sciensano holds historical collection of non-invasive pneumococcal isolates

Between 1995 and 2015, [name] (MD, PhD) led a team at Sciensano investigating the evolution of antibiotic resistance in NIPD isolates from CAP patients (as well as from children with acute otitis media). For 12 consecutive winter periods, his team collected between 300 and 500 clinical isolates using a network of 15 peripheral hospital-based laboratories distributed across the country. Consequently, we hold a collection of >5,000 strains for which extracted gDNA, complete phenotypic MIC profiles and associated metadata are already available (**Figure 4** for age distribution). This study, funded by Bayer, focused on antimicrobial resistance and did not routinely include serotyping.

This constitutes an extremely valuable collection that dates from before the introduction of pneumococcal vaccination programs. In the context of the proposed study, this collection would serve to retrospectively assess the impact of successive vaccination campaigns on serotype distribution among NIPD isolates in Belgium.

[figure not shown]

Figure 4. Age distribution of the patients for which cultures were included during the NIPD surveillance study in 2012-2013 using the same network of laboratories [24].

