1.6 Key points

From the information above, it is clear that:

- Current recommendations for vaccination and empiric treatment are strongly influenced by the current surveillance focus on IPD. Information on serotype distribution and drug resistance dynamics in NIPD is scarce. However, a discrepancy in serotype distribution between IPD and NIPD isolates is present in neighbouring countries.
- In Belgium, there was a recent (2015-2016) switch in the infant vaccination program to PCV10 and a recommended reversal to PCV13 in December 2018. The influence on serotype distributions in NIPD is unclear, although this information is essential in vaccine cost-effectiveness analyses [31].

2 Study aims

The main objective of this study is to generate insight in the serotype dynamics for NIPD in Belgium, in association with changing vaccination programs. We aim to serotype non-invasive *S. pneumoniae* isolates prospectively collected in Belgian routine laboratories, during a period of 20 months. Simultaneously, a similar characterisation study will be performed retrospectively on a selection of more than 5,000 NIPD strains collected between 1995 and 2014 in Belgium.

Additionally, this projects aims to do the surveillance of emerging serotypes, clones and drug resistances. Using Whole Genome Sequencing (WGS), the genetic divergences between IPD and NIPD isolates will also be studied, in collaboration with the National Reference Centre (NRC) for pneumococcal diseases (UZ Leuven, Belgium).

3 Type of study

This will be an observational study collecting data on *S. pneumoniae* serotypes causing NIPD in Belgium, in relation with changing vaccination programs.

4 Conducting the study

The study will be conducted by Sciensano in collaboration with the NRC for pneumococcal diseases and 12 peripheral clinical laboratories, which all agreed in writing to prospectively collect non-invasive *S. pneumoniae* samples in the framework of this study. These labs are geographically spread over Belgium to avoid clonal bias in sampling (**Table 1**).

Table 1. Peripheral network of participating clinical laboratories.

Hospital	Contact	City	
CHR Citadelle	Dr. [name]	Liège	
CHU Mont-Godinne	Dr. [name]	Yvoir	
ZNA	Dr. [name]	Antwerpen	
Virga-Jessaziekenhuis	Dr. [name]	Hasselt	
Hôpital de Jolimont	Dr. [name]	Haine-St.-Paul	
AZ Delta	Dr. [name]	Roeselare	
AZ St. Jan	Dr. [name]	Brugge	
AZ. Jan Palfijn	Dr. [name]	Gent	
Imeldaziekenhuis	Dr. [name]	Bonheiden	

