5.6 Whole-Genome Sequencing of selected isolates

Whole-Genome Sequencing (WGS) will be performed for multi-drug resistant and non-typeable strains or if clonality of the same serotypes originating from different, but geographically linked, patients needs to be assessed.

In this project, we budget the sequencing of 300 strains, the selection of which will be made in collaboration with the NRC for pneumococcal diseases to maximize genetic insights in the diversity of circulating IPD and NIPD serotypes.

For every selected strain, gDNA will be extracted using the automated MagCore™ platform (Atrida, NL) using standard procedures for gram-positive bacteria. Illumina MiSeq™ sequencing will be performed in-house, according to internally validated procedures. In brief, high-quality sequences are mapped onto a single reference genome, *S. pneumoniae* ATCC700669. We will use the bioinformatic pipeline designed by the NRC, to maximize the comparability with IPD isolates.

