6.2 Evaluation

Our final goal is to investigate Belgian trends in serotype distribution in the non-invasive pneumococcal population. The statistical data analysis will be performed with Stat10 software (Stata Statistical Software: Release 13. College Station, TX), in collaboration with Sciensano's Epidemiology Service.

Using data from the Prospective/Retrospective surveillance track:

- Chi-square trend analysis of circulating serotypes within the non-invasive *S. pneumoniae* population, integrating retrospective data (1995-2014) with prospectively collected data (2020-2022). Data will be compared with the serotype dynamics of IPD, annually published by the NRC for pneumococcal diseases.

- Measurement of association strength within each stratum of age, gender and infection type by the prevalence ratios with exact Fisher tests for statistical significance. Particular attention will be given to NeSP isolates, their association with patient type and their influence on drug resistance.
- Chi-square trend analysis of antimicrobial resistance for all tested drug classes, in relation to historic data (1995-2013) and in association with serotype.
- Integrating metadata with WGS, we will perform phylogenetic analysis of sequenced isolates in their national and international context [13,14], and identification of genetic determinants of antibiotic resistance.

7 Access to source data and data in general

Neither of the funding partners can have a role in data collection and interpretation. However, funding partners can request at any time intermediate results or reports. The final report will be put under a six months embargo before open access publishing in Summer 2023.

8 Monitoring and quality assurance

All laboratory analyses will be performed according to ISO15089 standards. An internal project board consisting [name] (MD, PhD), [name] (Ir, PhD), [name] (Ir., PhD) and [name] (MD, PhD) will monthly follow up experimental results.

9 Adverse events

Not applicable.

10 Ethics

Upon approval of the project by at least two contact partners, a general and specific ethical application will be filed, in collaboration with Sciensano's legal department and GDPR officer. Approval of local and ethical committees will be sought.

11 Budget

PERSONNEL				
	Description	% Effort dedicated to this study	Institutional salary (3 years)	TOTAL
	Coordinating Scientist	0.6 FTE	€ 276,372	€ 165,823.2
	Statistician	0.2 FTE	-*	€ 0

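### The between-period chi-square trend tests in section 6.2 ignore clustering of isolates by laboratory, so p-values for serotype and resistance shifts are too small to the extent that laboratory mix or laboratory effects change

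*Protocol*

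**What the plan says.** Section 6.2 of the protocol names three inferential methods:

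- For serotypes: "Chi-square trend analysis of circulating serotypes within the non-invasive" population, joining the 1995-2014 isolates to those of 2020-2022.
- For resistance: "Chi-square trend analysis of antimicrobial resistance for all tested drug classes", set against historical data.
- For associations: "Measurement of association strength within each stratum of age, gender and infection type" "by the prevalence ratios with exact Fisher tests for statistical significance".

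The strata are age, gender and infection type. Laboratory does not appear in 6.2, and section 6.1 states no design effect.

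The sampling is by laboratory. Section 4 describes "12 peripheral clinical laboratories, which all agreed in writing to prospectively collect" isolates, and section 4.1 takes up to 15 a month from each. Section 1.4 says that the historical collection came through "a network of 15 peripheral hospital-based laboratories distributed across the country".

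The protocol is aware of clonal linkage. Section 4 says: "These labs are geographically spread over Belgium to avoid clonal bias in sampling". Section 5.6 provides for sequencing "if clonality of the same serotypes originating from different, but geographically linked, patients needs to be assessed".

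**The concern.** Chi-square and Fisher tests count every isolate as a separate piece of evidence. Isolates from one laboratory share a catchment, a referral pattern, a culture practice and sometimes a circulating clone. A clone that is common around one or two laboratories in one period adds many isolates of the same serotype and resistance profile, and the tests read these as independent support for a national shift.

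At stake is whether a change is declared significant and linked to a vaccination programme. Section 6.1 makes a statistically significant shift between the two collections the first secondary objective. The tests are fixed in the protocol itself, so this is more than a detail left to an analysis plan.

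**Working it through.** The plan has no figure of its own for clustering. The check asks how far a nominal 5% two-period test departs from 5% when there is no true shift.

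**Inputs from the protocol**
- Prospective: 2,250 isolates (6.1) from 12 laboratories (4), so 2,250/12 = 187.5, taken as 188 per laboratory. Over 20 months this is about 9 per laboratory-month, in 12 × 20 = 240 laboratory-months.
- Historical: 150 isolates per uneven year (4.2) and 1,500 in total (6.1, 11), so ten years. From 15 laboratories (1.4) this is 100 per laboratory, or 10 in each of 15 × 10 = 150 laboratory-years.

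**Assumptions not in the protocol**
- ICC of 0.002 to 0.02.
- Even spread over laboratories.
- A two-period comparison in place of the trend test.

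**Formulas**
- Design effect in each period: D = 1 + (m − 1) × ICC, where m is the cluster size.
- Variance ratio: R = (D₁/n₁ + D₂/n₂) / (1/n₁ + 1/n₂).
- Actual error: 2 × [1 − Φ(1.96/√R)].

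**Example.** Take ICC 0.01 with correlation over the whole laboratory-period.
- D₁ = 1 + 187 × 0.01 = 2.87 and D₂ = 1 + 99 × 0.01 = 1.99.
- R = (2.87/2,256 + 1.99/1,500) / (1/2,256 + 1/1,500) = 2.34.
- 1.96/√2.34 = 1.28, so the error is 20%.

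**Case 1: laboratory effects independent between periods**

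| Correlation acts within | ICC 0.002 | 0.005 | 0.01 | 0.02 |
|---|---|---|---|---|
| Laboratory-period in both (12×188 v 15×100) | 8% | 13% | 20% | 31% |
| Laboratory-period prospective, laboratory-year historical (12×188 v 150×10) | 7% | 10% | 14% | 22% |
| Laboratory-year in both (24×94 v 150×10) | 6% | 8% | 10% | 15% |
| Laboratory-month prospective, laboratory-year historical (240×9 v 150×10) | 5% | 5% | 6% | 7% |

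Beta-binomial simulation with 40,000 replicates agrees with every row to within half a percentage point for a 50% class. The first row is nearly the same for classes of 5% and 7.5%.

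**Case 2: laboratory effects persist between periods.** With 12 laboratories in both periods, equal shares and fully stable effects, simulated error is 4.4-5.2% (1,500 v 1,500, ICC 0.001 to 0.05). If the 12 are a subset of the 15, the results at ICC 0.005, 0.01 and 0.02 are:
- all laboratory variance persisting, equal shares: about 6%, 7% and 8%;
- all persisting, unequal shares (assumed coefficient of variation about 0.5): about 8%, 10% and 15%;
- half persisting, equal shares: about 9%, 14% and 21%.

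**Fisher tests.** For a factor balanced within laboratories, such as sex, the simulated error of the corresponding unadjusted two-proportion test is 4.4-5.1%.

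**The case against.** Five points on the other side have weight.

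1. *The protocol gives no ICC.* A reader might infer that the planned p-values are simply wrong. The documents do not support that, because neither the presence nor the size of the error can be derived from them.
2. *Stable laboratory differences cancel.* Section 1.4 describes the 2012-2013 survey as using the same network, so overlap is plausible. This stands. However, cancellation needs the same laboratories, equal shares and stable effects, whereas the protocol gives 15 v 12 laboratories, a monthly cap with no quota, and historical sampling that is not by laboratory.
3. *A clone that comes and goes does not tie 1995 isolates to those of 2013.* This stands too, and it is why the 8-31% row is an upper case and the range starts near 5%.
4. *The design already limits dependence.* Isolates are unduplicated, the historical draw is random, laboratories are spread out, and sequencing can identify clones. These steps reduce repeats and improve coverage, but none puts laboratory into a test. Equally, the text seeks to avoid clonal bias and makes sequencing conditional, so one should not infer that the protocol expects local clones.
5. *A large shift would survive.* If the PCV13 serotypes, 50% in 6.1, fell to 40%, z is about 6.0 unadjusted (2,256 v 1,500). Dividing by √R gives about 4.0 at ICC 0.01 (R = 2.34) and 3.2 at ICC 0.02 (R = 3.68). Smaller shifts, rare serotypes and resistance trends are more exposed.

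A reader might also infer that the prevalence-ratio intervals are too narrow. Section 6.2 specifies no such interval, so nothing is claimed about one.

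**Conclusion.** The point holds for the between-period chi-square tests of serotype and resistance. They assume independence, the sampling is by laboratory, the protocol recognises possible clonal linkage, and no test accounts for laboratory. To the extent that laboratory mix or effects differ between periods, the p-values are too small.

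The size depends on the assumptions: about 5-7% actual error if correlation acts only within laboratory-month and laboratory-year, and up to 8-31% if it acts over the whole laboratory-period, both at assumed ICCs of 0.002-0.02. It is about nominal with the same laboratories, equal shares and stable effects. These figures are for a two-period test, so they are a guide to the trend test and not an exact result for it.

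The Fisher tests within strata are a lesser matter. They are affected mainly where the factor, non-encapsulated strains or resistance is concentrated in a few laboratories.

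This is a change that should be made, as an inexpensive improvement to the stated methods.

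**What to change.** In section 6.2, account for laboratory in the between-period analyses and base inference about shifts on the result:

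- Use log-binomial or Poisson regression of serotype class or resistance on period or year, with variance clustered by laboratory and a small-sample correction for 12-15 clusters. Laboratory and laboratory-by-period random effects are an alternative.
- For rare serotypes, use an exact test stratified by laboratory.
- The unadjusted chi-square and Fisher results may be reported alongside.

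The cost is a change of wording and some programming, with no new isolates or laboratory work. The submitting laboratory is known for each prospective isolate. For the historical isolates, laboratory of origin must be carried in the metadata; section 1.4 says that metadata exist but does not list them. The price is wider intervals and some loss of nominal significance.

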- Section 5.3. *S. pneumoniae* confirmation was changed to match with methods in the NRC, towards "All isolates will be tested for susceptibility to optochin and bile solubility. In case of doubt or negative reaction, a slide agglutination test (e.g. Slidex pneumo-Kit□, BioMérieux) as well as their MALDI-TOF (Biotyper, Bruker) profile will be examined."
- Section 5.4; Genetic capsular typing is replaced by FT-IR based typing." Capsular typing is performed according to the traditional Quellung reaction. However, in this project we will investigate the use of Fourier transform infrared spectroscopy to predict the serotype of the most prevalent serotypes [32,33]. It has been reported that discriminatory biochemical fingerprints observed on FT-IR spectra have been consistently correlated with sugar-based coating structures that reflect strain variation. This will allow to perform capsular typing on a medium-throughput scale (96-well plate format), at less than €5 consumable cost per sample. The test will be validated, and published, in collaboration with the National Reference Center for Pneumococcal diseases (UZ Leuven, Belgium)."
- Section 5.5. The table with antibiotics to be tested was adapted, to match the drugs tested at the NRC.
- Section 5.6; WGS data analyses will be done using the pipeline designed by the NRC at UZLeuven
